Nox T3s data will be uploaded for review by a scoring team at Elite Sleep Professionals, or similar organization of registered polysomnographic technologists. The sleep apnea tests will not be reviewed by a physician. Study participants who are eligible for the CPAP adherence intervention will not be told of the severity of OSA until completion of study participation so that any decision to adhere to CPAP is not influenced by OSA severity from a single-night HSAT, which typically underestimates the disease severity.³⁸⁻⁴⁰ Nox T3s reports will be provided to the participant and the clinical team at the time the participant exits participation in this study. Based upon prior studies in this population^{4-6 17} we anticipate that about 20% of the 60 participants with completed OSA tests may be excluded based on these criteria, yielding approximately 48 participants for the Aim 1 adherence program adaptation.

Existing SCOUTS2 adherence intervention, implemented for participants

Participants who meet criteria for a diagnosis of OSA will be set up with CPAP on the next available night after the HSAT by study staff led by the study's sleep technologist, who will provide mask fitting and CPAP exposure during the daytime prior to the 1st night of CPAP use. The CPAP device (AirSense™ 11 AutoSet, ResMed) includes an auto-titrator that can adjust the delivered pressure between 4 to 20 cm of water to eliminate obstructive events. Pressure settings may be narrowed. All Aim 1 participants may receive 3 basic supportive treatments to approximate the care provided after a sleep clinic or in-hospital diagnosis of OSA: 1) education on OSA and the importance of CPAP treatment for improved sleep and vascular health; 2) standard inpatient CPAP support from respiratory therapy and IPR nurses for mask placement and adjustments; and 3) outpatient access to a national durable medical equipment (DME) company, for issues that may arise with CPAP at home. Participants may also receive 3 behavioral adherence interventions:

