(i) CPAP technical support: Initial mask fitting will be completed by the study's sleep technologist on the IPR unit rather than by respiratory therapists, if possible. The study's sleep technologist will initially ensure adequate mask fit without air leak, trial different CPAP mask interfaces for patient comfort and provide education or adjustments to address adherence issues.⁴¹ A member of the SCOUTS3 team led by the study's sleep technologist may then meet ideally daily with participants over the first three days of initiating CPAP to assess perception of treatment and symptom-related treatment response;^{42,43} complete a 7-item questionnaire of common adverse symptoms associated with CPAP (appended);⁴⁴ make mask type/size or device adjustments, as needed; and provide training to participants and CPAP partners to improve skills involved with mask placement and device maintenance. For participants with non-acceptance of CPAP over the first night, a standardized desensitization program may be implemented by the sleep technologist. Persistent problems with CPAP use, mask fit, or high residual respiratory events may be discussed between the sleep technologist and Co-I [name], a board-certified sleep medicine physician.

(ii) MET with individualized verbal and written feedback: In-person MET sessions during IPR and telephone sessions after IPR discharge will also be completed by a sleep coach. The in-person MET sessions will occur typically within 3 days of starting CPAP and again after about 3 to 5 days if the participant remains on IPR. The 1st in-person MET session will focus on subjective assessment of CPAP use, barriers and facilitators of use, assessment of motivation and confidence for use, decisional balance and feedback. The 2nd MET session will focus on subjective appraisals of CPAP adherence, reinforcement of changes with treatment, and review of treatment goals. The post-discharge MET phone sessions will begin approximately two weeks after discharge, then monthly during the 3 months of CPAP therapy and will last approximately 30-60 minutes. Consistent with prior research in stroke patients on the dose of MET needed, the goal will be to deliver a total of 4 hours of MET counseling over the 3 months of CPAP therapy.^{45,46} In the spirit of MET, the participants will dictate the pace of the sessions. We may alter the frequency, duration, and content of the sessions based on participant feedback.

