For aphasic participants, the sleep coach will use published recommendations to adapt MET sessions for people with stroke-related aphasia, including strategies to enhance language comprehension and facilitate

expression⁴⁷⁻⁴⁹ and patient-specific strategies recommended by the study participant's speech-language pathologists on the IPR unit. Patients with more severe aphasia with complete incomprehension are not typically admitted to IPR. The MET for aphasic participants will include two face-to-face sessions during IPR, each lasting about 30 to 60 minutes, and one ~20-minute phone session with inclusion of the CPAP partner, when possible. Face-to-face sessions will incorporate MET components used in non-aphasic participants but will focus on information exchange through visual aids, exploring potential barriers to CPAP use through enhanced communication and goal setting.⁵⁰ MET sessions may be bolstered by individualized written and visual feedback regarding the OSA testing, potential vascular consequences, and CPAP download data illustrating the effectiveness of treatment in reducing respiratory events.

Fidelity for the MET sessions will be evaluated in multiple ways. Some MET sessions will be recorded, uploaded for processing, and reviewed via the cloud-based and HIPAA-compliant Lyssn platform, which supports training and quality assurance by providing automated transcription and fidelity feedback from a session recording. The recordings are processed through the system's artificial intelligence analytics tool and automatically transcribed via speech-to-text transcription. The platform will produce reports of each session, including general and specific metrics for MET. The sessions will be evaluated through the Lyssn platform and feedback reports will be provided to the sleep coach. Consultants, [name] and [name], may also review ~20% of the counseling sessions for non-aphasic participants utilizing a MET checklist to provide feedback to the sleep coach via quarterly virtual meetings.²⁰ Co-I [name], who has adapted motivational counseling to improve adherence to therapy in other populations,⁵¹ may review ~20% of the recordings of aphasic participants utilizing a modified MET checklist.

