- The participant will be set-up by a study team member with a single-night sleep test on night 1 after enrollment to assess for the presence of OSA using the Nox T3 or T3s™ portable home sleep apnea test monitor (includes the T3/T3s device, a nasal pressure cannula, wrist-based oximeter unit with finger probe, and two respiratory inductance plethysmography belts for the chest and abdomen). The Nox T3 may be repeated up to 2 times in the rare cases of failed recordings or self-reported poor sleep if the participant is willing to repeat the study.

Visit 3: (in-hospital and in-person during inpatient rehabilitation)

- Participants will be informed of their eligibility in the study approximately 1 day after the sleep apnea study (if the respiratory event index or REI, the number of apneas and hypopneas per hour of recording, ≥ 5 with 3% desaturation criteria for hypopneas, and the absence of predominant central sleep apnea, defined as central apnea index $< 50\%$ of total REI).
- Study participants will be informed the day after the testing but will not be told of the severity of OSA until completion of study participation so that any decision to adhere to CPAP is not influenced by OSA severity.

Visit 4: (in-hospital and in-person during inpatient rehabilitation)

- Participants with a diagnosis of OSA will be set up with CPAP on the next available night after the sleep apnea test by the study's sleep team led by the study's sleep technologist, who will provide mask fitting and CPAP exposure during the daytime prior to the 1st night of CPAP use.
- Magnetic masks will not be used in participants with implantable devices or metallic objects affected by magnets.
- The CPAP device (AirSense™ 11 AutoSet, ResMed) includes an auto-tritrator that adjusts the delivered pressure between 4 to 20 cm of water to eliminate obstructive events.

Visits 5-7 (in-hospital and in-person during inpatient rehabilitation)

- Study's sleep team will meet daily with participants over the first three days of initiating CPAP to assess perception of treatment and symptom-related treatment response; complete a 7-item questionnaire of common adverse symptoms associated with CPAP; make mask type/size or device adjustments, as needed; and provide training to participants and CPAP partners to improve skills involved with mask placement and device maintenance.

Visit 8 (in-hospital and in-person during inpatient rehabilitation)

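### Does the MET feedback on sleep apnea testing undo the plan's rule that participants are not told their OSA severity?

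*Combined protocol and SAP*

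**What the plan says.** Under Screening for OSA, participants who qualify for CPAP "will not be told of the severity of OSA until completion of study participation". The reason given is that the choice to use CPAP should not be swayed by a severity figure from one night of home testing, which the protocol says tends to read low. The same section holds back the written report: "Nox T3s reports will be provided to the participant and the clinical team at the time the participant exits participation in this study". Visit 3 of the AIM 1 overview repeats the rule and adds what participants do learn: "Participants will be informed of their eligibility in the study approximately 1 day after the sleep apnea study".

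Item (ii) of the existing SCOUTS2 intervention is headed "MET with individualized verbal and written feedback". On timing it says "The in-person MET sessions will occur typically within 3 days of starting CPAP", with phone sessions after discharge. The paragraph on aphasic participants ends: "MET sessions may be bolstered by individualized written and visual feedback regarding the OSA testing, potential vascular consequences, and CPAP download data", the last of these "illustrating the effectiveness of treatment in reducing respiratory events". No sentence there cites the concealment rule. Item (ii) also says "We may alter the frequency, duration, and content of the sessions based on participant feedback".

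Under Statistical analysis, the primary endpoint is qualitative (interview themes) and the secondary endpoint is mean nightly CPAP use over three months. Demographic, stroke-related and sleep-related correlates of CPAP use are to be examined, but the sleep-related ones are not named.

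**The concern.** One section withholds a piece of information until exit, and another lets the sleep coach give individualized feedback about the test that produced it, months before exit. Because participants already know that they qualified, the obvious item left to individualize is the test result. Showing that treatment lowers respiratory events also invites comparison with the untreated level, which in this study is the REI from the home test. The plan's wording for CPAP partners is narrower, since it speaks of the diagnosis and not of the testing.

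If coaches read the sentence this way, some participants would know their severity and others would not. The stated purpose of the concealment would be lost for those who knew. If REI were among the sleep-related factors, its association with CPAP use would mix two groups. In uninformed participants severity can act only through symptoms and treatment response. In informed participants it can also act through knowledge of the result. The scope is unclear too: the sentence closes the paragraph on aphasia, while the heading of item (ii) points to all MET.

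**Working it through.** The plan gives no figure to reproduce, so the check sets the passages side by side.

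1. **Type of rule.** The concealment statement is a prohibition on one named item (severity), with a stated end point (completion of participation). It appears in two sections. The feedback sentence is optional and names three broad topics: the testing, vascular consequences and CPAP downloads. It does not mention severity, REI or the sleep test report. A specific prohibition ordinarily limits a general permission without being repeated beside it.

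2. **Can both be followed?** Yes. A coach can explain what was tested and that OSA was found, which participants in effect learn at Visit 3. Downloads are on-treatment data. The mHealth section lists hours of use, mask seal and residual AHI among the data shown in myAir, and residual AHI can illustrate effectiveness without a baseline value. Nothing in the documents puts the baseline REI into a download.

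3. **Session content.** The in-person MET descriptions in item (ii) cover reported use, barriers, motivation, decisional balance, feedback and goals. Visits 9 and 10 in the AIM 1 overview do not list a test result or a severity category for participants.

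4. **Occasions before exit.** Sessions are counted from the visit schedule and the aphasia paragraph.
   - Non-aphasic: 2 inpatient (Visits 9 and 10) + 2 phone (Visits 13 and 14) = 4. With discharge before Visit 10: 1 + 2 = 3.
   - Aphasic: 2 face-to-face + 1 phone = 3. If the second inpatient session is also lost to early discharge: 1 + 1 = 2.
   - All precede the end-of-study assessment at Visit 17. The monthly phone wording in item (ii) could add sessions. How written or visual material would reach a participant by phone is not stated, although the heading of item (ii) also allows verbal feedback.

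   The feedback is assigned to no particular session, so these counts are upper limits on opportunity and say nothing about how often severity would be disclosed.

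5. **What a disclosure would affect.** The study has one arm, so there is no between-arm contrast to bias. Mean CPAP use describes the package as delivered, and MET feedback belongs to that package. No route to the qualitative themes is shown. What remains is the exploratory association with CPAP use. It would be affected only if a coach departed from the concealment rule and REI was chosen as a factor. That association already pools changing versions of the intervention, because session content may be altered as the study proceeds.

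**The case for a change.** The best case for a change is that the concealment is deliberate, is stated twice, and could be secured with one sentence. Nothing beside the feedback sentence tells the coach which text governs, and no order of precedence is given. An optional permission could be used unevenly, which is worse for an exploratory association than uniform disclosure or uniform concealment. The package is also the study's product and is meant for a later randomized trial, so its content ought to be explicit.

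Part of this stands. The missing cross-reference is real, and so is the unclear scope of the sentence. The rest does not carry through. Uneven disclosure requires staff to set aside a categorical instruction because of a sentence that never mentions severity. The contrast with the partner wording compares sentences written for different audiences, and nothing shows the difference was meant. The content of the package for the later trial is what this adaptation study is designed to settle. Barring before/after comparisons or logging disclosures would go further than the ambiguity requires.

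**Conclusion.** This is an ambiguity and not a contradiction, and no change to the plan is needed. Followed as written, with the concealment rule binding on MET feedback, the plan keeps severity from participants until exit and leaves both endpoints sound. The size of any effect is unknown, because the documents give neither a disclosure rate nor an effect of disclosure on use. The only route to harm is doubly conditional and ends in one exploratory association with a factor the plan does not name.

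The conclusion assumes that staff treat the twice-stated prohibition as governing and that test feedback in MET stays with the presence of OSA and on-treatment data. If the sponsor in fact intends coaches to give the REI or a severity category, the concealment statements would no longer describe the study and this conclusion would not hold. Nothing in the documents states that intention. A cross-reference beside the feedback sentence, with a word on whether it covers all MET, would be good editing but would not alter the conduct or analysis described here.

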Stroke patients on Neurology and PM&R will be screened for eligibility and interested eligible patients will be consented. While on either of two IPR units at the University of Washington (UW) or Harborview Medical Center (HMC), consented participants will be tested for OSA, and then, within a single-arm study, exposed to a multicomponent CPAP adherence intervention, beginning during IPR and extending for 3 months. Throughout the intervention exposure, participants' CPAP use will be monitored, and input regarding the intervention will be sought from the participants, CPAP partners (ideally bedpartners, but if not available, then those who can provide support to the patient), and the research team implementing the intervention (sleep technologist, research coordinator, sleep coach, nurses). Semi-structured interviews will take place to obtain formal feedback from participants at three time points during their 3-month intervention. Data will be reviewed in meetings with the study team and a patient advisory board, and adaptations will be devised and then implemented within the next batch of Aim 1 participants. Through this iterative process that includes input from important stakeholders, the behavioral intervention will be adapted for use among stroke patients.

Participants and eligibility criteria

60 adult patients recovering from acute stroke within the past 30 days will be recruited during inpatient acute or IPR (2 IPR units) stroke stays.

Inclusion criteria include:

1. Age 18 years or older
2. Head CT or brain MRI demonstrating an acute ischemic infarction or intraparenchymal hemorrhage within past 30 days
3. Person providing consent (patient or legally authorized representative) able to be consented in English or Spanish.

Exclusion criteria include:

1. Unable to obtain informed consent from participant or surrogate in English or Spanish
2. Incarcerated
3. Known pregnancy
4. Current mechanical ventilation, tracheostomy or supplemental oxygen use > 4L/min
5. Current use of positive airway pressure or use within 14 days prior to stroke
6. History of pneumothorax, bullous emphysema or other serious co-morbid conditions which limit CPAP use
7. Stroke related to tumors, vascular malformations or subarachnoid hemorrhage

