8. Active use of sedative drugs that can interfere with testing for obstructive sleep apnea (OSA) including any benzodiazepine, barbiturate, general anesthesia, or conscious sedation within the prior 48 hours of the planned portable sleep apnea study
9. Anticipated inpatient rehabilitation length of stay < 3 nights
10. Co-morbid conditions that limit OSA testing or CPAP use in the judgement of the study team

Recruitment and consent of study participants

Patients: We will review medical records of the acute stroke and/or IPR patients to identify those who may be eligible to participate. We request a HIPAA waiver for this chart review. Patients will be approached in person. The study will be described by a study team member, which may be supplemented by an introductory video (appended). All questions will be answered. Before participation in any study related activity, written informed consent will be obtained from the participant or legally authorized representative (LAR). Assent will be used if appropriate for those who need an LAR. Written documentation of assent will not be collected. eConsent may be used. A copy of the informed consent instrument will be provided to each participant.

CPAP partners: Partners will be selected by participants as the bedpartner or the person most likely to be able to provide support for CPAP use. The purpose of the study will be described to the CPAP partner, in person, by secure video, or by phone. All questions will be answered. Written informed consent will be obtained directly from the partner. eConsent may be used. Not all participants will identify a CPAP partner for participation.

Identification of advisory board members and clinical team members

The advisory board members may include previous participants in the study team's research on CPAP for stroke patients. No advisory board member will be a current participant in one of the study team's studies. CPAP partners of previous study participants may also be included in the advisory board. Advisory board members are not subjects of the proposed research. They will be used for consultation and feedback on study design and implementation issues. Similarly, clinical and research team members will be identified based on their contact with a research subject. They may be asked questions about the implementation of the study procedures but are not research subjects themselves.

Baseline and rehabilitation discharge assessments

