(iii) Phone follow-up for adherence feedback and self-management skills: The research coordinator will call participants approximately monthly to encourage use and resolve problems with therapy.²¹ In an effort to improve CPAP tolerance and minimize side effects, the research coordinator will provide encouragement and basic education, review persistent outpatient CPAP-related issues with co-I [name] and refer participants to a durable medical equipment (DME) company when needed for device or mask adjustments.

90-day end-of-study assessment

After approximately 90 ± 14 days from enrollment, phone evaluations by study will be obtained by a certified investigator, including the mRS-9Q, questions about sleep duration and quality, and the Zarit Burden Interview. We anticipate the time to complete assessments will be between 10 to 15 minutes.

AIM 1: SCOUTS3 Single-arm study— Research design and methods overview.

Visit 1: (in-hospital and in-person during inpatient rehabilitation)

- Stroke participants will be asked to provide contact information for themselves and their primary caregiver or family member.
- Contact information will be obtained for a "CPAP partner," either a bed partner or caregiver who can assist with CPAP use
- A brief (~10 minutes) set of questionnaires and assessments will be obtained for baseline stroke severity and functional disability by a certified investigator.
- Neck circumference will be measured by a study team investigator.
- The medical record will be reviewed and key data extracted, including medical history, neuroimaging and any note for common implantable devices that can be affected by magnets (pacemakers and intracranial shunt).
- Participants will be screened for any personal or bed-partner medical implants that can be affected by magnets (i.e., pacemakers, implantable cardioverter defibrillators (ICD), neurostimulators, cerebrospinal fluid (CSF) shunts, insulin/infusion pumps) or metallic implants/objects containing ferromagnetic material (i.e., aneurysm clips/flow disruption devices, embolic coils, stents, valves, electrodes, implants to restore hearing or balance with implanted magnets, hearing implants, metallic splinters in the eye). If participant has any such medical implants or metallic implants/objects, a note will be made in the database to

refrain from using magnet-containing masks.

Visit 2: (in-hospital and in-person during inpatient rehabilitation)

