6. I use the CPAP treatment because it feels good to use CPAP.	Strongly agree 5	Agree 4	Undecided 3	Disagree 2	Strongly disagree 1
7. I use the CPAP treatment because other people say I have to.	Strongly agree 5	Agree 4	Undecided 3	Disagree 2	Strongly disagree 1
8. I use the CPAP treatment because the personnel say I have to.	Strongly agree 5	Agree 4	Undecided 3	Disagree 2	Strongly disagree 1
9. I use the CPAP treatment because I have to.	Strongly agree 5	Agree 4	Undecided 3	Disagree 2	Strongly disagree 1

Prestroke sleep duration & Quality (baseline in reference to pre-stroke state)

Sleep duration:

During the month prior to the stroke, excluding naps, how many hours of actual sleep did you get at night (or day, if you work at night) on average?

RESPONSE OPTIONS: < 6 hours per night, 6-8 hours per night, > 8 hours per night

Sleep quality:

During the month prior to your stroke, how would you rate your sleep quality overall?

RESPONSE OPTIONS: 1 = excellent, 2 = very good, 3 = good, 4 = fair, 5 = poor

Prestroke sleep duration & Quality (90 day)

Sleep duration:

During the past month, excluding naps, how many hours of actual sleep did you get at night (or day, if you work at night) on average?

RESPONSE OPTIONS: < 6 hours per night, 6-8 hours per night, > 8 hours per night

Sleep quality:

During the past month, how would you rate your sleep quality overall?

RESPONSE OPTIONS: 1 = excellent, 2 = very good, 3 = good, 4 = fair, 5 = poor

After Nox T3 sleep apnea test

Was the T3 qualifying for CPAP treatment (REI ≥ 5 and CAI was $<50\%$ of REI)?

RESPONSE OPTIONS: yes, no, sufficient data not obtained

If yes,

Did the participant try CPAP for at least one night?

RESPONSE OPTIONS: yes, no

Participant phone number:

Participant email:

Participant address:

Did the participant identify a CPAP partner?

RESPONSE OPTIONS: yes, no

If yes,

CPAP partner name

CPAP partner phone number

7 adverse symptoms of CPAP (after night 1, night 2 and night 3 of using CPAP)

“Did you have problems with CPAP last night?”

No **Yes**

“We would like you to answer yes or no to some **side effects** of CPAP that people may experience.”

List of 7 adverse events or problems associated with CPAP use

Patient receives a score of one point for the presence of any complaints within each category, producing a total possible side effect score of seven points.

Mouth dryness

Nasal symptoms

Eye problems

Claustrophobia

Noise problems

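### Visit 1 asks about magnet-sensitive implants in the bed partner, but on a plain reading the database note and the Visit 4 mask rule act only on the participant's own implants

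*Combined protocol and SAP*

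**What the plan says.** The relevant text is in the section AIM 1: SCOUTS3 Single-arm study.

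- **Visit 1, question asked.** "Participants will be screened for any personal or bed-partner medical implants that can be affected by magnets". The sentence goes on to list examples of devices and metallic objects. The participant is asked about both people; the bed partner is not examined or questioned directly.
- **Visit 1, resulting action.** "If participant has any such medical implants or metallic implants/objects, a note will be made in the database to" "refrain from using magnet-containing masks".
- **Visit 4, mask rule at CPAP set-up.** "Magnetic masks will not be used in participants with implantable devices or metallic objects affected by magnets".

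Three other places give context. The Overview describes the intervention as "beginning during IPR and extending for 3 months". The phone follow-up component allows the coordinator to "refer participants to a durable medical equipment (DME) company when needed for device or mask adjustments". On who counts as a CPAP partner, the recruitment section says: "Partners will be selected by participants as the bedpartner or the person most likely to be able to provide support for CPAP use". A CPAP partner may therefore be someone other than the bed partner.

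**The concern.** The question covers two people, while each of the two action sentences names one. The protocol chose to ask about bed partners, so the answer was presumably meant to inform the choice of mask. Followed literally, however, the mask rule permits a magnetic mask when the bed partner has, say, a pacemaker or a CSF shunt and the participant has no such device.

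What is at stake is the safety of someone who may sleep beside the mask. Treatment runs for 3 months and masks can be changed along the way, so the question does not end with the first fitting. That bed-sharing would mostly begin after discharge is a reasonable assumption, but the protocol does not say so. Some exposure could come earlier: CPAP partners, who may be bed partners, are trained in mask placement during the first three days of CPAP.

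**Working it through.** No formula applies to the main point. The check is to set the question against the two actions and trace each possible answer.

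**Inputs.** The Visit 1 question (participant or bed partner), the Visit 1 note trigger (participant) and the Visit 4 bar (participants).

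**Two readings of the note.** The plain reading takes the subject of the sentence, the participant, at face value. The wider reading lets the back-reference in the condition reach all the implants just asked about, including a bed partner's.

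| Who has an implant | Note, plain reading | Note, wider reading | Visit 4 bar |
|---|---|---|---|
| Neither | No | No | No |
| Participant only | Yes | Yes | Yes |
| Both | Yes | Yes | Yes |
| Bed partner only | **No** | Yes | **No** |

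The first three rows come out the same whether or not the bed-partner question is asked, because a participant's own implant already triggers both actions. Only the last row depends on that question. There, the plain reading gives no instruction, and the wider reading gives a note that Visit 4 does not match.

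**Is the gap filled elsewhere?**

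- The Visit 1 chart review looks for implants in the participant's medical record, which cannot be expected to cover the bed partner.
- The exclusion criteria do not mention magnet-sensitive implants.
- The mask-fitting text under the existing SCOUTS2 intervention, the CPAP risk text under Potential Risks to participants, and Protection Against Risk contain no magnet rule.

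No other place in the text reviewed says what to do when only the bed partner has an implant.

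**How many participants could the rule concern?** Under Screening for OSA, the plan anticipates that about 20% of 60 tested participants may be excluded: 60 × (1 − 0.20) = 48 expected to start CPAP. This is an expectation. If fewer are excluded, more start, up to 60. The share with a bed partner who has such an implant, and the share who would be given a magnetic mask, are not stated, so no frequency follows.

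**The case against.** The strongest reply is that the text can be read without a gap. The note sentence comes straight after the question, and its back-reference may be meant to pick up everything just asked about. Staff who have just recorded a bed partner's pacemaker may well write the note.

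That reading is possible, and the text does not rule it out. It is the weaker one grammatically: the subject is the participant, and a person does not ordinarily have someone else's implant. It also leaves Visit 4 unrepaired, since the sentence that governs the fitting still names participants only. The two sentences need aligning on either reading.

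A second reply is that the instruction may sit elsewhere. The consent pages are not in the text reviewed, and no implant-screening form is among the appended forms. This stands, and it confines the point to what the available text says. The appended field that asks "Did the participant identify a CPAP partner" settles nothing either way, because it concerns the CPAP partner, who need not be the bed partner.

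A reader might go further and infer that bed partners will in fact be exposed to magnetic masks, or that the study has no safeguard for them. The documents do not support that. They give no mask types, magnet strengths or implant rates, staff may avoid such masks in practice, and the risk itself is inferred only from the fact that the question is asked.

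**Conclusion.** The point holds as a minor inconsistency of wording. On the plain reading, the text reviewed does not bar a magnetic mask when only the bed partner has a magnet-sensitive implant. On the wider reading, Visit 4 remains narrower than the Visit 1 note. No endpoint, sample size or analysis is affected.

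The size cannot be estimated. The 48 expected to start CPAP should not be taken as an upper limit on those concerned; the planned maximum is 60, and neither number estimates how often the case would arise.

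The conclusion rests on two things: that the bed-partner question was meant to guide mask choice, and that no instruction exists in documents not seen here. Confidence is high about what the available text says, and lower about the study's full set of procedures.

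**What to change.** Change two sentences.

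- **Visit 1.** In the note sentence, replace the subject with *the participant or bed partner* and leave the rest as it stands.
- **Visit 4.** Recast the rule so that magnetic masks are barred whenever *the participant or bed partner* has a device or object that magnets affect.

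Use *bed partner* in both places, matching the Visit 1 question, because the CPAP partner may be a different person. If an implant-screening form exists outside the public document, check that its wording agrees.

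The cost is the two edits and fewer mask options for participants whose bed partner has such an implant. The list at Visit 1 is broad (it includes stents, valves, coils and hearing implants), so how many participants that would be is unknown.
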